8.11. Atopic Dermatitis Control Tool

The Atopic Dermatitis Control Tool (ADCT) is a 6-question PRO instrument used to detect change of disease activity in a person over time. There are six main areas that assess the multi-dimensional aspects of disease control over the course of a week, scored between 0-4, with a minimum score of 0 and a maximum score of 24. A higher score indicates lower AD control. A change of 5 points is the threshold for meaningful within person change, where a decrease of 5 or more points indicates clinically relevant improvement of AD control and an increase of 5 or more points indicates a clinically relevant worsening of AD control (Pariser, 2020).

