- Percentage of participants achieving EASI-50, EASI-75 and EASI-90
- Percentage of participants achieving IGA 0 or 1, with and without a 2-point improvement from baseline
- Percentage of participants achieving BSA-50, and BSA-75

Other exploratory endpoints will be evaluated at Weeks 2, 4, 8, 12 and 16 (unless otherwise specified) and are:

- Percentage of participants achieving vIGA of 0 or 1 with a ≥ 2 Point Improvement from screening.

- Mean absolute change and percentage change from Screening in EASI Score.
- Percentage of participants requiring topical antimicrobial or systemic antibiotic treatment for skin infections by Week 16.
- Changes from baseline in SF-12 Mental Component Score (MCS) and Physical Component Score (PCS) at Weeks 4, 12 and 16.
- Changes from baseline in HADS anxiety and depression scores at Weeks 4, 12 and 16.
- Changes from baseline in ADCT scores at Weeks 4, 12 and 16.
- Daily changes from baseline in the PP-NRS and SD-NRS (Timescale: Days 2 to 140).
- Percentage of participants achieving a reduction of ≥ 2 , ≥ 4 in the PP-NRS, of those with a score of ≥ 2 , ≥ 4 at baseline daily from Day 2 to 112.
- Percentage of participants achieving a reduction of ≥ 2 in SD-NRS score, of those with a score of ≥ 2 at baseline daily from Day 2 to 112.

Note that analyses of the other exploratory endpoints including the following biomarkers exploratory endpoints will be addressed in a separate analysis plan and will not be further discussed in this document:

- Changes from baseline in eosinophils at Weeks 2, 16 and 20.
- Changes from baseline in serum immune protein markers including IgE at Week 16.
- Changes from baseline in immune cell RNA profile at Weeks 2, 16 and 20.

5 Study Methods

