5.3.3.13 Atopic Dermatitis Control Tool (ADCT)

The Atopic Dermatitis Control Tool (ADCT) is a 6-question PRO instrument used to detect change of disease activity in a person over time. There are six main areas that assess the multi-dimensional aspects of disease control over the course of a week, scored between 0-4. ADCT scores range from a minimum score of 0 and a maximum score of 24. A higher score indicates lower AD control.

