9.5.1.1 Continuous Exploratory Endpoints

Continuous exploratory endpoints:

- Mean absolute change and percentage change from Screening in EASI Score.
- Changes from baseline in SF-12 MCS and PCS scores.
- Changes from baseline in HADS anxiety and depression scores.
- Changes from baseline in ADCT scores.
- Daily changes from baseline in the PP-NRS and SD-NRS (Timescale: Days 2 to 112).

The population summary measure of interest will be the mean value in each treatment group.

Endpoints other than PP-NRS and SD-NRS will be summarized as described in [Section 8](#).

Daily PP-NRS and SD-NRS endpoints will be listed and plotted.

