- 3 = Very often indeed
- 2 = Quite often
- 1 = Not very often
- 0 = Not at all

Question 14:

- 0 = Often
- 1 = Sometimes
- 2 = Not often
- 3 = Very seldom

HADS Anxiety and Depression Total Scores

The HADS anxiety total score is the sum of the 7 anxiety scores. The HADS depression total score is the sum of the 7 depression scores.

Total scores for anxiety and depression ranges from 0 to 21 and classifies as:

- 8-10 = Mild
- 11-14 = Moderate
- 15-21 = Severe

23 Appendix 9: Atopic Dermatitis Control Tool

The ADCT consists of 6 questions:

1. Over the last week, how would you rate your eczema-related symptoms (for example, itching, dry skin, skin rash)?
2. Over the last week, how many days did you have intense episodes of itching because of your eczema?
3. Over the last week, how bothered have you been by your eczema?
4. Over the last week, how many nights did you have trouble falling or staying asleep because of your eczema?
5. Over the last week, how much did your eczema affect your daily activities?
6. Over the last week, how much did your eczema affect your mood or emotions?

Questions 1 is scored as:

- 0 = None
- 1 = Mild
- 2 = Moderate
- 3 = Severe
- 4 = Very severe

Question 2 is scored as:

- 3 = Not at all
- 2 = 1-2 days
- 1 = 3-4 days
- 0 = 5-6 days
- 0 = Every day

Question 3 is scored as:

- 0 = Not at all
- 1 = A little
- 2 = Moderately
- 3 = Very
- 4 = Extremely

Question 4 are scored as:

- 3 = No nights
- 2 = 1-2 nights
- 1 = 3-4 nights
- 0 = 5-6 nights
- 0 = Every night

Questions 5 and 6 are scored as:

- 0 = Not at all
- 1 = A little
- 2 = Moderately
- 3 = A lot
- 4 = Extremely

The ADCT total score is the sum of the 6 ADCT questions and ranges from 0 to 24.

24 Appendix 10: MedDRA Internationally Agreed Order for System Organ Class

The internationally agreed SOC order to be used for medical history and AE summary tables is provided in [Table 5](#).

Table 5 MedDRA Internationally Agreed SOC Order

Order Number	System Organ Class
1	Infections and infestations
2	Neoplasms benign, malignant and unspecified (incl cysts and polyps)
3	Blood and lymphatic system disorders
4	Immune system disorders
5	Endocrine disorders
6	Metabolism and nutrition disorders
7	Psychiatric disorders
8	Nervous system disorders
9	Eye disorders
10	Ear and labyrinth disorders
11	Cardiac disorders
12	Vascular disorders
13	Respiratory, thoracic and mediastinal disorders
14	Gastrointestinal disorders
15	Hepatobiliary disorders

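### SAP Appendix 9 scores ADCT items 2 and 4 backwards and caps them at 3, so the plain sum cannot be the stated 0–24 score

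*SAP*

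**What the plan says.** Protocol 8.11 describes six areas, "scored between 0-4, with a minimum score of 0 and a maximum score of 24", with higher totals meaning poorer control. It adds that "a decrease of 5 or more points indicates clinically relevant improvement of AD control". SAP 5.3.3.13 repeats the item range, the total range ("ADCT scores range from a minimum score of 0 and a maximum score of 24") and the direction ("A higher score indicates lower AD control").

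SAP Section 23 (Appendix 9) then gives the scoring, item by item:

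- Items 1, 3, 5 and 6: 0 for the best answer up to 4 for the worst.
- Item 2, days with intense itching: 3 for none, 2 for 1–2 days, 1 for 3–4 days, 0 for 5–6 days, 0 for every day.
- Item 4, nights with sleep trouble: the same pattern of 3, 2, 1, 0, 0.

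It closes with: "The ADCT total score is the sum of the 6 ADCT questions and ranges from 0 to 24". No recoding or rescaling comes before the sum.

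The score is used for an exploratory endpoint, "Changes from baseline in ADCT scores at Weeks 4, 12 and 16" (SAP 4.2; also SAP 9.5.1.1 and Protocol Table 11-3). It feeds Table 14.2.52, Figures 14.2.52.1 and 14.2.52.2, and Listing 16.2.6.16.

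**The concern.** Four items rise as the disease worsens and two fall, and all six are added together. The total then has no consistent direction: better itch and sleep push it up while better symptoms, bother, daily activities and mood push it down. Separately, giving the two worst answers on items 2 and 4 the same code caps those items at 3, so the maximum of 24 stated in the same appendix cannot be reached.

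Itch and sleep are the two inverted items, and the trial follows both closely through PP-NRS and SD-NRS. A treatment that worked mainly on them could show a rising ADCT total, which would be read as loss of control. The 5-point within-person change given in Protocol 8.11 also loses its meaning, because it belongs to a 0–24 score on which every item points the same way.

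**Working it through.** **Inputs.** Item codes and the summing rule are from SAP Appendix 9. The intended item range (0–4), total range (0–24) and direction (higher is worse) are from SAP 5.3.3.13 and Protocol 8.11. Items are listed in order 1 to 6.

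**Stated range.** With all six items scored 0–4, the minimum is 6 × 0 = 0 and the maximum is 6 × 4 = 24. This reproduces the stated 0–24.

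**Range from the Appendix 9 codes.** The maximum is 4 + 3 + 4 + 3 + 4 + 4 = 22. Enumerating all 5⁶ = 15,625 answer patterns confirms an attainable range of 0 to 22. The end points do not correspond to best and worst control:

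- 22 requires the worst answers on items 1, 3, 5 and 6 together with no itch days and no bad nights.
- 0 requires the best answers on those four items together with itch and sleep trouble on at least 5 days and nights of the week.

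**Participants at the same level on every item** (level 0 = best answer, 4 = worst):

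| Level on all items | Appendix 9 total | Intended total |
|---|---|---|
| 0 | 0+3+0+3+0+0 = 6 | 0 |
| 1 | 1+2+1+2+1+1 = 8 | 6 |
| 2 | 2+1+2+1+2+2 = 10 | 12 |
| 3 | 3+0+3+0+3+3 = 12 | 18 |
| 4 | 4+0+4+0+4+4 = 16 | 24 |

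The distance from best to worst is 16 − 6 = 10 points instead of 24.

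**Changes from baseline:**

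| Improvement | Appendix 9 | Intended | Share lost |
|---|---|---|---|
| All items, level 4 to 0 | 6 − 16 = −10 | −24 | 14/24 = 58% |
| All items, one level, starting from level 3 or better | −2 | −6 | 4/6 = 67% |
| All items, level 4 to 3 | 12 − 16 = −4 | −6 | 2/6 = 33% |
| All items, level 2 to 0 | 6 − 10 = −4 | −12 | 8/12 = 67% |
| Items 2 and 4 only, level 4 to 0 | +6 | −8 | sign reversed |
| Items 1, 3, 5, 6 from 3 to 1; items 2 and 4 from level 4 to 0 | (1+3+1+3+1+1) − (3+0+3+0+3+3) = −2 | (1+0+1+0+1+1) − (3+4+3+4+3+3) = −16 | 14/16 = 88% |

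In the fourth row, a participant who goes from the middle answer to the best answer on every item would miss the 5-point mark in Protocol 8.11.

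**Could something else in the documents correct it?**

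- SAP 5.3.3.2 to 5.3.3.6 say that EASI, BSA, vIGA, SCORAD and POEM come ready-made in the supplied data, and the SF-12 appendix names scoring software. SAP 5.3.3.13 says neither for ADCT, so Appendix 9 is the only scoring instruction given.
- SAP Section 13 and Section 6 of the Cohort 4 addendum list no change to ADCT scoring.
- SAP Appendix 5 (POEM) asks closely similar questions on itchy days and disturbed nights and scores them forward, 0 to 4.
- SAP Appendix 8 (HADS) has items worded in both directions and sets the codes item by item so that higher is always worse. The ADCT appendix does not.
- The 3, 2, 1, 0, 0 pattern appears in full in two separate items, so it is unlikely to come from text extraction.

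**The case against.** The strongest reply is about consequence. ADCT change is exploratory, and Protocol 11.4.5 limits exploratory endpoints to summaries without inference. It appears in one table, two figures and a listing, none marked for top-level results. No ADCT responder analysis is planned, so the 5-point threshold bears only on how a reader interprets the means and waterfall plot. All of this stands and limits the importance of the point.

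A second reply is that the loss is partial and depends on the answer pattern. From worst to best on every item, the four forward items contribute −16 and the two reversed items give back 6, an offset of 6/16 = 37.5%, so the total still falls. The −2 against −16 example is at the unfavourable end. The coding also applies equally to placebo, so the effect on a between-group difference depends on item-level changes that nobody knows in advance. That is fair. It still leaves 58% of the worst-to-best change missing, and the sign wrong when only itch and sleep improve.

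A third reply is that the programs may not follow the appendix: the SAP body already has the right range and direction, ADCT is captured electronically, and the listing of individual components would expose a reversal. This is possible, but the documents do not say where the total is computed, and the only written instruction is the faulty one.

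**Conclusion.** Appendix 9 is wrong as written. It contradicts its own range (22 against 24) and contradicts SAP 5.3.3.13 and Protocol 8.11 on item range and direction. If followed, the span from best to worst control shrinks from 24 points to 10, a uniform improvement loses between 33% and 67% of its size, and improvement confined to itch and sleep shows as worsening. The range and direction errors follow directly from the listed codes. The effect on reported results assumes that the total is derived from Appendix 9 rather than delivered already scored. Damage is confined to the exploratory ADCT outputs. It should be corrected because those outputs would be invalid and the correction is small.

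**What to change.** In SAP Appendix 9, score items 2 and 4 as 0 = none, 1 = 1–2, 2 = 3–4, 3 = 5–6 and 4 = every day or night. The plain sum then runs from 0 to 24 with higher meaning worse control, as the appendix's own range, SAP 5.3.3.13 and Protocol 8.11 require.

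State in SAP 5.3.3.13 whether the total is derived in the analysis datasets or taken from the supplied data. Check the derivation program with two test records: best answers throughout must give 0, and worst answers throughout must give 24.

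The cost is ten code lines in one appendix and a short SAP amendment or documented note, since the SAP is final at version 2.0. If ADCT outputs have already been produced from the current codes, Table 14.2.52, its two figures and the derived score in Listing 16.2.6.16 need rerunning. No new data are needed.

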6 Summary of Changes from the Protocol..... 11

7 Bibliography 11

8 Appendix 1: List of Tables, Figures and Listings 12

 8.1 Efficacy 12

 8.1.1 Tables 12

 8.1.2 Figures..... 12

9 Appendix 2: List of [name] patients..... 13

Table of Tables

Table 1: Summary of Changes from the Protocol and the main SAP 11

2 Abbreviations and Definitions

BSA	Body Surface Area
BMI	Body Mass Index
CI	Confidence Intervals
DPS	Data Point Set
EASI	Eczema Area and Severity Index
FAS	Full Analysis Set
PS	Propensity Score
SD	Standard Deviation
SAP	Statistical Analysis Plan
vIGA	Validated Investigator Global Assessment

3 Introduction

The purpose of this SAP Cohort 4 Addendum is to provide information that, together with the main SAP, is necessary to perform the required cohort 4 specific statistical analyses of study EDP1815-207. It also defines the cohort 4 specific TFLs to be included in the final clinical study report according to the protocol. The SAP addendum is based upon, and assumes familiarity, with the study protocol, version 5.0, dated 25-Apr-2022.

Only additional information specific to cohort 4 analyses or different from what was stated in the main SAP is included in this SAP addendum. The main study SAP should be referred to for all derivations, estimand definitions and model specifications.

Changes to the analyses described in the protocol or the main SAP other than those already listed in the main SAP are summarised in Section 0.

If a future protocol amendment necessitates a substantial change to the statistical analysis of the study data, this SAP Addendum will be amended accordingly. The content of this SAP Addendum is compatible with the ICH E9 Guidance document.

4 Efficacy Analyses

4.1 Pooling of Placebo Cohorts

For cohort 4 efficacy analyses, cohort 4 placebo group and set of 35 matched placebo participants from cohorts 1-3 will be pooled into a single 'cohort 4 matched placebo' group and will be used as a common control group for the cohort 4 EDP1815 treatment group.

As a sensitivity analysis, the cohort 4 EDP1815 treatment group will also be compared to the cohort 4 placebo group in all relevant analyses.

4.1.1 Selection of Matched Placebo

Selection of matched placebo participants will be made separately by the unblinded team before cohort 4 DBL but close enough to ensure that data needed for analysis is cleaned and will not change for all cohort 4 participants.

Only pre-treatment data (covariates from screening or baseline) of cohorts 1-3 placebo participants and cohort 4 participants and treatment assignments of cohort 4 participants will be provided to the unblinded team for analysis.

The process management details and team responsibilities are described in an interim analysis process plan.

35 placebo participants will be selected from cohorts 1-3. The group will include 5 to 7 participants with mild vIGA score and 3 to 5 participants with severe vIGA score to match cohort 4 vIGA frequencies.

Propensity scores

Propensity scores (PS) will be estimated by a logistic regression model. The treatment assignment (binary: 0 for placebo and 1 for active) is regressed through covariates.

The following covariates will be selected for initial model:

- Categorical: vIGA, sex, region (North America, rest of the world)
- Continuous: BMI, BSA, EASI score

Covariates will come from the last pre-treatment assessment which can be screening, baseline or unscheduled visit. To ensure the fit of the model sex or region may be excluded from covariates list.

Main matching algorithm

Each patient in active treatment group of cohort 4 will be matched with one placebo patient from cohort 1-3 using optimal matching to minimize overall calliper distance of matched pairs (Austin 2011). Initially calliper distance will be set to 0.25 (SD of logit(PS)) and may be increased to get more matches and ensure better balance of covariates.

From all matched pairs, only pairs with loose* vIGA match will be selected.

From the loose matched pairs, 5 pairs with lowest logit(PS) difference where cohort 4 matched subject has mild vIGA score and 3 pairs with lowest logit(PS) difference where cohort 4 matched subject has severe vIGA score will be selected to ensure minimum requested frequency of mild and severe vIGA.

Another 27 pairs will be selected from the remaining loose matched pairs with the least logit(PS) difference to ensure that best matched candidates are chosen.

If more than 7 pairs with mild vIGA cohort 4 matched subjects or 5 pairs with severe vIGA cohort 4 matched subjects will be selected, excess pairs with highest logit(PS) difference will be replaced by pairs with moderate vIGA cohort 4 matched subjects (chosen from remaining pairs with lowest logit(PS) difference).

Placebo participants from these pairs will be considered as matched group from cohorts 1-3 and included in the cohort 4 matched placebo group in addition to cohort 4 placebo participants.

* Loose match keeps mild – moderate and moderate – severe matches in addition to exact matches and only discards the matches between mild and severe in either group.

Balance diagnostics

After selection is complete, balance diagnostics will be performed. Balance of all covariates will be compared for before matching and after matching scenarios.

Graphics will be presented for:

- continuous covariates - side by side box plot
- binary/categorical covariates - grouped bar-plot to compare frequencies

Also, standardized differences will be calculated:

- continuous covariates:

$$d = \frac{\bar{x}_{TRT} - \bar{x}_{CON}}{\sqrt{\frac{S_{TRT}^2 + S_{CON}^2}{2}}}$$

here \bar{x}_{TRT} , S_{TRT}^2 is sample mean and sample variance of treatment group.

- binary/categorical covariates:

$$d = \frac{\hat{p}_{TRT} - \hat{p}_{CON}}{\sqrt{\frac{\hat{p}_{TRT}(1-\hat{p}_{TRT}) + \hat{p}_{CON}(1-\hat{p}_{CON})}{2}}}$$

here \hat{p}_{TRT} is response rate in treated group. For variables (e.g. region) with multiple categories, “d” will be measured for each category.

PS matching will be assessed against pre and post matching balance diagnostics. The calliper distance may be modified accordingly until an acceptable balance is achieved across the covariates or some covariates may be excluded.

In case of the main algorithm failure the alternative algorithm will be used.

Alternative matching algorithm

Perform optimal fixed ratio matching for cohort 4 placebo participants with cohort 4 EDP1815 participants. Exact matching for vIGA covariate should be considered.

Remaining unmatched 35 EDP1815 participants from cohort 4 will be matched (using similar fixed ratio optimal matching) with 35 placebos from cohorts 1-3. Placebo participants from these pairs will be considered as matched group and analysed in the cohort 4 matched placebo group.

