11.8. Determination of Sample Size

Cohorts 1-3

The sample size was calculated using the assumption that data from the placebo participants in the three cohorts can be pooled prior to comparison with the EDP1815 treatment groups. No adjustments for multiple testing have been made.

The primary efficacy endpoint is the achievement of EASI-50 at Week 16. The pooled placebo response rate is estimated to be approximately 25% and a doubling of this to 50% for EDP1815 would be considered as clinically meaningful.

Using a two-sided test at the 5% level of significance, 58 participants in each treatment group would give 80% power to detect a difference in one of the EDP1815 cohorts compared to the pooled placebo group. There would also be more than 90% power to compare the pooled EDP1815 6.4×10^{11} daily dose or all the EDP1815 group to the pooled placebo group.

Under the assumption of a 20% drop-out of participants prior to Week 16 this will require a total of at least 73 participants to be enrolled in each treatment group. In order to allow for the 3:1 randomization in each cohort this has been adjusted to 75 participants per treatment group to give a total of 300 participants recruited. With 75 EDP1815 participants and 25 placebo participants in each of the three cohorts.

Cohort 4

Using the same assumptions relating to the placebo rate, clinically meaningful difference, significance level, and drop-out rate as above for Cohorts 1-3, approximately 70 participants are required in each of the EDP1815 8.0×10^{10} and Cohort 4 Matched Placebo groups to provide approximately 80% power in detecting a difference between EDP1815 and placebo in Cohort 4.

In order to allow 50% of the placebo control group to be concurrent controls and 50% to be historic matched controls from Cohorts 1-3, a 2:1 randomization will be used to enroll 70 EDP1815 8.0×10^{10} subjects and 35 placebo participants to Cohort 4.

If sensitivity analyses indicate that pooling of the Cohort 4 placebo group with the Cohort 1-3 matched placebo data is inappropriate, then the power of the comparison between the Cohort 4

EDP1815 and placebo groups is approximately 65% if only Cohort 4 placebo participants could be used in the treatment comparisons.

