4.3.1 Primary Efficacy Estimand

The primary efficacy estimand will be the effect of cohort 4 EDP1815 compared to the cohort 4 matched placebo group on the percentage of participants achieving EASI-50 at Week 16. The population summary measure of interest will be the odds ratio between active EDP1815 treatment group and matched placebo.

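### The main Cohort 4 matching rule balances the borrowed placebos against at most half of the EDP1815 arm, although all 70 participants enter the comparison

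*SAP*

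**What the plan says.** Protocol 11.8 sets the Cohort 4 allocation: "a 2:1 randomization will be used to enroll 70 EDP1815" participants and 35 placebo. A further 35 placebos are borrowed from Cohorts 1-3, which have about 75.

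SAP Addendum 4.1.1 gives the main algorithm:
- "Each patient in active treatment group of cohort 4 will be matched with one placebo patient from cohort 1-3", by optimal matching with an initial calliper of 0.25 SD of logit(PS).
- Mild-severe pairs are discarded.
- The 5 closest pairs with a mild Cohort 4 member and the 3 closest with a severe one are kept.
- "Another 27 pairs will be selected from the remaining loose matched pairs with the least logit(PS) difference", subject to caps of 7 mild and 5 severe.
- Only the placebos of the kept pairs are carried forward.

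Addendum 4.1 makes these 35 plus the 35 concurrent placebos the control for the Cohort 4 EDP1815 group. Addendum 4.3.1 agrees: "The primary efficacy estimand will be the effect of cohort 4 EDP1815 compared to the cohort 4 matched placebo group". The full analysis population (main SAP 7.1.1.2) is everyone randomised.

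The Addendum also has an alternative, used only if the main algorithm fails. Cohort 4 placebos are first matched to Cohort 4 EDP1815 participants. Then "Remaining unmatched 35 EDP1815 participants from cohort 4 will be matched" to 35 Cohort 1-3 placebos.

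**The concern.** Matching is meant to make the borrowed placebos comparable with the arm they control. Here they are made comparable only with the EDP1815 participants in the kept pairs, who lie where the two enrolment periods overlap. The other EDP1815 participants stay in the analysis. Nothing in the Addendum restricts the active arm to the kept partners, weights it, or keeps the pairing in the model.

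If Cohort 4 differs at baseline from Cohorts 1-3, part of that difference stays in the primary Cohort 4 comparison. The outcome model adjusts for vIGA and EASI. BSA is in the propensity score but is not a candidate model covariate (main SAP 7.2). BMI, sex and region enter only if Cohorts 1-3 selected them (main SAP 9.2, Addendum 4.2).

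**Working it through.** **Plan's own figures.** Inputs from Protocol 11.8: "The pooled placebo response rate is estimated to be approximately 25% and a doubling of this to 50% for EDP1815"; "Using a two-sided test at the 5% level of significance"; "Under the assumption of a 20% drop-out of participants prior to Week 16". So 70 × 0.8 = 56 and 35 × 0.8 = 28 evaluable. Unpooled normal approximation: power = Φ(0.25/SE − 1.96).
- 56 v 56: SE = √(0.1875/56 + 0.25/56) = 0.0884; 0.25/0.0884 = 2.83; power 80.7% (stated: about 80%). The pooled-variance form gives 78.8%.
- 28 placebo v 56 active: SE = √(0.1875/28 + 0.25/56) = 0.1056; 2.37; power 65.8% (stated: about 65%). The pooled form gives 59.9%.

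These figures reproduce. The point concerns who is matched, not N.

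**Count.** 5 + 3 + 27 = 35 pairs kept for 70 EDP1815 participants, so 70 − 35 = 35 have no retained match.

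**Balance by simulation** (400 runs per scenario; 70 active, 35 concurrent, 75 earlier placebos; calliper, loose vIGA filter, quotas and caps as written). Assumptions not in the documents: vIGA mix 17/71/12%, correlated EASI-like and BSA-like scores, and a severity shift between enrolment periods. In 9% to 19% of runs the quotas or the total of 35 could not be met; averages are over the other runs. The alternative was run without a calliper or exact vIGA matching. Standardised differences in the severity score:

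| Assumed shift (SD) | 0 | 0.3 | 0.5 | 0.8 |
|---|---|---|---|---|
| Before matching | 0.00 | 0.28 | 0.45 | 0.72 |
| Borrowed 35 v their 35 partners | 0.00 | 0.01 | 0.02 | 0.01 |
| Borrowed 35 v all 70 EDP1815 | 0.01 | 0.16 | 0.25 | 0.40 |
| Borrowed 35 v the 35 EDP1815 left out | 0.02 | 0.31 | 0.49 | 0.83 |
| Pooled 70 placebos v all 70, main rule | 0.00 | 0.08 | 0.12 | 0.19 |
| Pooled 70 placebos v all 70, alternative | 0.00 | 0.00 | 0.03 | 0.09 |

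Against all 70, the main rule removes 1 − 0.25/0.45, about 45%, of the raw difference. Pooling halves the remainder: 0.25/2 = 0.125, against 0.12 simulated.

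**Cause.** About 48 to 59 pairs survive the calliper and vIGA filter. So 11 to 22 of the 70 never have a usable pair, and 13 to 24 more are dropped in the cut to 35. To separate these, the same rule was run with the 35 surviving pairs chosen at random. With pre-match differences of about 0.39 (EASI), 0.40 (BSA) and 0.52 (region), the borrowed 35 differ from all 70 by:
- closest pairs: 0.20/0.22/0.22
- random pairs: 0.23/0.24/0.22
- all surviving pairs (about 49): 0.22/0.22/0.21

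The closeness step contributes essentially nothing. The remainder comes from calliper-limited 1:1 matching of 70 to about 75.

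**Trial-to-trial balance of the pooled control.** Root-mean-square standardised difference (EASI/BSA/region) at the larger shift: main 0.17/0.17/0.18, alternative 0.13/0.13/0.12. With no shift: about 0.15 against 0.08.

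**Effect on the odds ratio** (500 runs; pre-match 0.40/0.40/0.54). Null log OR about +0.04, so OR = e^0.04 = 1.04. Upper-tail rejection is about 3.4% against a nominal 2.5%. The Monte Carlo error at 2.5% is √(0.025 × 0.975/500) = 0.7 points, so this excess is not clearly separated from chance. For scale, 50% v 25% is an odds ratio of 3 (log 1.10), and the standard error of a log OR at 56 v 56 and 25% is √(2/(56 × 0.1875)) = 0.44.

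**The case against.** A reader might infer that the sentence keeping the closest pairs is itself the defect. It is not: random choice among surviving pairs does no better. With effectively no calliper, closeness helps (0.23/0.26/0.31 against 0.32/0.34/0.47 for random).

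A reader might also infer that matching is the only protection against differences between enrolment periods. The documents do not support that:
- Half of the control is concurrent and randomised.
- vIGA and EASI are modelled.
- Cohort 4 recruitment may be limited by vIGA stratum (Protocol 6.11).
- The within-Cohort-4 comparison and the Bayesian borrowing analysis (Addendum 4.3.3) do not use the matched set. The former was added because of concern about placebo similarity (Addendum 6).

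These points stand, and they limit the size of the problem.

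The planned balance diagnostics are a weaker defence. No threshold is set. The text does not say whether the treated side is all 70 or the kept 35, and against the 35 the balance would look excellent. The stated remedies are to change the calliper or drop covariates. In a simpler run without vIGA quotas at a 0.5 SD shift, widening the calliper to 0.5 moved the logit(PS) difference against all 70 from 0.34 to 0.40. Failure of the main algorithm, which triggers the alternative, is not defined.

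Finally, the alternative is less fully specified: no calliper, no vIGA quotas, exact vIGA matching only to be considered, and exactly 35 participants assumed to remain. That is a fair objection to adopting it unchanged.

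**Conclusion.** The point holds as a design improvement. The main rule borrows placebos that resemble at most half of the arm they control, while the Addendum already contains a rule that covers all of it at the same N and power.

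The size is modest. It depends on an assumed baseline difference between enrolment periods: at about 0.4 SD, roughly half remains in the borrowed 35 and about 0.1 in the pooled 70. Because vIGA and EASI are modelled, what reaches the odds ratio comes mainly through BSA and any of region, BMI or sex that Cohorts 1-3 did not select. A log OR shift of +0.04 is about a tenth of its standard error (0.04/0.44).

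A reader might go further and conclude that the Cohort 4 result is materially biased. The documents give no baseline distributions to support that, and with no cohort difference the mean bias is nil. The simulations show direction and approximate size only.

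**What to change.** - Make the alternative algorithm the main one. Or choose the 35 borrowed placebos to minimise the standardised differences of the pooled 70 placebos against all 70 EDP1815 participants.
- Carry over the vIGA quotas or require exact vIGA matching, and word the rule for the numbers actually enrolled rather than exactly 35 and 35.
- Compute the balance diagnostics for the pooled placebo group against all Cohort 4 EDP1815 participants, with a threshold set beforehand, and define what counts as failure.

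The cost is a short re-specification of the alternative, and some individual pairs will be less close. Sample size and power do not change. Selection uses pre-treatment data only, but the Cohort 1-3 placebo outcomes are unblinded after their own lock (main SAP 7.4.5), so the rule should be fixed in a dated amendment before the selection is run.
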